2. STUDY SCHEDULE AND TIMELINE

IBSOS is a prospective, randomized, multi-site clinical trial comparing three types of psychotherapy delivered in an individual format for severely affected adults with IBS. After a four-week baseline data collection period, participants will be randomly assigned to receive either four-session self-administered CBT, 10-session therapist-administered CBT or a control condition emphasizing support and education (allocation 1:1:1). The acute treatment phase will last 10 weeks. Participants will undergo follow-up examinations two weeks after treatment ends (week 12) and three, six, nine, and 12 months after the end of treatment.

IBSOS requires the expeditious enrollment of a sufficient number of participants to ensure the statistical power and generalization of study results. This trial plans to recruit 480 participants over an approximately four-year treatment delivery period. Assuming a relatively conservative pre randomization dropout rate of 25%, each site will need to phone telephone screen approximately 150 participants per year and enroll (consent) 75 in order to meet yearly recruitment quotas of 60 randomized participants at each site.

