APPENDIX 5: Adverse Event Reporting

Completing the Adverse Event Case Report Form (CRF)

- Each adverse event must be reported using the Adverse Event (AE) CRF. If necessary, multiple AE CRF forms may be used for participants.
- After completing the header fields, the clinician should write a brief description of the event on the AE CRF and use the standard definitions provided to indicate:
 - (a) the maximum severity of the AE
 - (b) the current status of the AE
 - (c) date of onset of the AE and, if AE has been resolved, date of resolution
 - (d) whether the AE was expected or unexpected the likelihood that the AE is related to the study treatment intervention.

These ratings are described in detail below.

If a participant did not experience an AE at the end of his/her study period (including follow-up), the clinician will indicate this on the AE CRF. In this case, the clinician will not fill out any other fields on the AE CRF except for the header fields, the Source Document Language field, and Form Completion Status field (filled in as 'Form Completed as Required'). There should be at least one AE CRF completed for each participant, even if a participant did not experience an adverse event during the course of the protocol.

AE Severity Rating

The clinician will rate the severity of each AE using a four-category scale. These categories are defined below. This rating should represent the maximum severity of the adverse event. For example, a participant may report multiple headache events over a short period of time or a prolonged period of chest pain that may vary in intensity. The clinician should provide a rating of the most severe episode of headache or a rating of the chest pain at its maximum severity. The numerical rating of the appropriate category should be recorded in the box marked "Severity."

- 1. Mild: Does not interfere with participant's usual function
- 2. Moderate: Interferes to some extent with participant's usual function
- 3. Severe: Interferes significantly with participant's usual function
- 4. Life-Threatening: Poses a significant threat to the life or functioning of the participant

It should be noted that judgments of AE severity should be independent of judgments regarding whether or not an AE is considered "serious." The term "severe" is typically used to describe the intensity (severity) of an event (as in mild, moderate, or severe pain); the event itself may be of regarded as medically benign (such as severe migraine

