Examples of noncompliance arise if a participant fails to attend two consecutive MC-CBT or S-CBT sessions, or three consecutive EDU sessions without a reason deemed appropriate by his or her therapist and site PI. Non-compliance with homework is not regarded as an acceptable basis for withdrawal.

4. **Administrative error** — Participants who do not meet all study inclusion or exclusion criteria may enter the study in error.

For example, a participant who does not disclose concurrent targeted psychotherapy for IBS or the presence of a medical condition that makes it unsafe or impractical for the participant to continue may be withdrawn at the PI's discretion. These participants may be replaced because they would not have satisfied eligibility criteria had the participant fully disclosed information regarding health status at the time eligibility was determined.

			Page 1 of 2
DATA COLLECTI	ON FORMS S	CHEDULE	00-00-00
ST	UDY IBSOS1 BOOK 1		
NOTE: The columns are marked with an "X" to indicate data and evaluation	ns required at each visit.	PRE-TREATMENT BASELINE	PREMATURE DISCONTINUATION
eData/HAND-ENTERED FORMS	Frontier Form #/ Reference		
IBS0S1 Study Participant Intake Form	QLW01	×	
IBS - Symptom Severity Scale	QLW03	×	
TEV- BL	QLW10	×	
IBSOS Comorbid Disease Form	QLW13	×	
MD Rating - Baseline	QLW15	×	
Concomitant Medications/Supplements and Non-Drug Therapies	CMW1	×	
IBS Module (IBS-PRO)	QLW14	×	
IBSOS1 Study Participant Economic Form	QLW06	×	
FMBS	QLW12	×	
Euroqol EQ- 5D	QLW02	×	
Adverse Events	IBS0021		×
Off Study / Drop Out	IBS1601		×
Missed Visit	ST0010		
Death Form	SP1411		
FLIPS FORMS	Frontier Form #/ Reference		
IBS - LOC	ibsloc	×	
IBS SE Questionnaire	ibsse	×	
bSS	bss	×	
PCSQ-2 Item	pcsq2	×	
IBS-QOL Instrument	ibsqol	X	
McGill - SF	mcgsf	×	
The SF - 12 Health Survey	sf12	×	
Restorative Activities	restact	×	
SOMS-7	soms7	×	
ASI	asi	×	
NSI	vsi	X	
Continued on page 2.			

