The PI and Site Investigators continually monitor safety issues at his/her site and report any problem to the Administrative Core at the University at Buffalo. As noted in the Chapter on Trial Governance, the IBSOS will identify a safety officer who functions as an independent evaluator (external to the study) of all adverse events (AEs), both serious and non-serious. In the case of this unmasked trial, the safety officer will work with the investigators to assure that the event is fully documented. Safety officers also review adverse event data to assess if the frequency of the AEs changes dramatically from baseline during treatment delivery phase of the trial. This change could be across the study or a change in the AE profile at a specific site.

Exclusions

Persons with medical or psychological contraindications will be deemed ineligible to be enrolled.

Institutional Review

Prior to study implementation, the protocol, informed consent forms, and all advertising materials must be approved by the IRB of each participating study site. All protocol amendments effecting the safety and welfare of study participants must be approved by the IRB prior to implementation. The study site PI is responsible for all submission documents and for periodic review reports required by the IRB.

Data Security and Confidentiality

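### The safety officer's AE-frequency review compares with an undefined baseline, across the study or at a site, and does not name the randomised arm as a level of comparison

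*Protocol*

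**What the plan says.** Protocol Appendix 9 (Protocol review and study monitoring) gives an external safety officer two tasks: to evaluate every AE, and to review AE frequency. On the second it says: "Safety officers also review adverse event data to assess if the frequency of the AEs changes dramatically from baseline during treatment delivery phase". The levels at which to look follow: "This change could be across the study or a change in the AE profile at a specific site". The same paragraph describes the trial as unmasked.

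Appendix 5 governs recording: "Each adverse event must be reported using the Adverse Event (AE) CRF", and "There should be at least one AE CRF completed for each participant", even when no event occurred. It gives no date from which AEs are to be recorded.

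In the Appendix 7 schedule for Book 1 (pre-treatment), the row "Adverse Events IBS0021" is empty under baseline and marked only under premature discontinuation. The AE rows of Books 2 and 3 follow the same pattern, with no treatment week and no follow-up visit marked.

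Section 2 gives the design: "After a four-week baseline data collection period", participants are randomised 1:1:1 to three arms. Of treatment it says "The acute treatment phase will last 10 weeks"; 12 months of follow-up come after that. Section 3.4 lists AE occurrence as a secondary endpoint.

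**The concern.** The review sentence fixes a comparator (before versus during) and two levels (study, site). Both are weaker than what the design offers. A concurrent attention-control arm was randomised alongside the two CBT arms, and the safety officer is not said to be masked, yet the sentence does not point to arm.

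Three consequences follow if it is applied as worded:

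- Pooling the arms dilutes a harm that belongs to one therapy. Looking by site does not help, because each site enrols to all three arms (Section 5.1 stratifies allocation by site).
- A before-after change mixes any therapy effect with the passage of time and with differences in how closely participants are asked about events.
- With no defined baseline, window or denominator, two people could apply the sentence to the same data and reach different answers.

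The frequency review also names only the treatment delivery phase, although Appendix 5 expects AE recording to run through follow-up.

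**Working it through.** The protocol states no AE rate, threshold or safety power, so there is no figure to reproduce. The dilution result needs no assumed rate; the power and exposure figures do.

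**Inputs from the protocol.** 480 participants, 240 per site (Section 4.1); allocation 1:1:1 (Section 2), hence 480/3 = 160 per arm, as Section 7.4 also states; baseline 4 weeks and treatment 10 weeks (Section 2).

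**1. Dilution.** Let p be the background risk and RR the true risk ratio in one arm, with the other two unaffected.

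Pooled risk = (p·RR + p + p)/3, so pooled ratio = 1 + (RR − 1)/3.

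| True RR in one arm | Ratio seen when pooled |
|---|---|
| 1.5 | 1.17 |
| 2 | 1.33 |
| 3 | 1.67 |

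This holds at any p, overall and within a site if the arms are balanced there. Example with p = 10% (assumed) and RR = 2: the affected arm has 160 × 0.20 = 32 participants with an AE and each other arm 160 × 0.10 = 16. Pooled, that is 64/480 = 13.3% against 10%, a ratio of 1.33. Affected arm against control it is 32 versus 16, a ratio of 2.0.

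**2. What dilution does to detection (illustration only).** Two-sided 5% comparison of two proportions, true doubling in one arm. The pooled before-after look is treated as two independent samples of 480, a simplification because the same people contribute to both periods.

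| Assumed background risk | By arm, 160 vs 160 | Pooled, 480 vs 480 |
|---|---|---|
| 2% | 18% | 10% |
| 5% | 40% | 20% |
| 10% | 71% | 36% |
| 20% | 98% | 69% |

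The arm comparison has more power in every row despite using fewer people. Large harms can still show when pooled: a tripling at 10% background gives 86% pooled and over 99% by arm.

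**3. Unequal windows (conditional).** Suppose 4 weeks of baseline are compared with 10 weeks of treatment without a rate.

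- Event counts at a constant weekly rate: 10/4 = 2.5 times as many in treatment, with no true change.
- Participants with at least one AE: (1 − exp(−10w))/(1 − exp(−4w)), where w is the weekly rate. At w = 0.5% this is 2.46; at w = 5% it is 2.17.

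**4. Is a baseline AE frequency available?** Appendix 7 schedules none. Appendix 5 requires every AE to be reported but does not say from when. A baseline frequency is therefore undefined and has no scheduled ascertainment. That is as far as the text goes.

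**The case against.** Several stronger readings are tempting, and the protocol does not support them.

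- **A reader might infer that baseline AEs are not collected.** The empty baseline cell does not show this. The AE form is unmarked at every scheduled visit in all three books, which fits the event-driven reporting of Appendix 5, and the form is included in the baseline book. By the same logic no AEs would be collected during treatment either.
- **A reader might infer that arm is excluded.** The sentence on levels says what the change could be, which is not exclusive. The trial is unmasked, AE occurrence is an endpoint of a three-arm trial, and the DSMB reviews interim data and safety. A monitoring plan (Appendix 3) and a governance chapter (Appendix 9) are mentioned but not shown, and by-arm tables may be specified there.
- **A reader might infer that this is the only safety check.** It is additional to individual evaluation of every AE, to ratings of severity, expectedness and relatedness, and to continual monitoring by investigators.
- **A reader might infer that a one-arm harm would go undetected.** The tripling example shows otherwise, and since the review is qualitative with no threshold, power is only a yardstick.
- **A reader might take the 2.5-fold inflation as certain.** It needs raw counts, whereas the text says frequency. It also needs a participant-level reading of the treatment delivery phase; Sections 2 and 4.3 use a similar term for the roughly four-year delivery period of the whole trial.

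Appendix 9 also expects no particular risk from either psychosocial treatment, so the stakes are modest.

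These objections limit the claim but do not remove it. The comparison that is written down is still a pooled before-after one with an undefined reference, and the randomised comparison is not named.

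**Conclusion.** The point holds as a cheap improvement to safety monitoring. It does not show that monitoring fails. The stated frequency review lacks a defined baseline, window and denominator and does not name arm. Read literally, it reduces a one-arm excess to one third (a risk ratio of 2 appears as 1.33) and cannot tell a therapy effect from time or ascertainment. The one-third result assumes three equal arms, harm in one only, and equal background frequency in the two periods. It does not depend on the AE rate. The exposure artefact, up to 2.5-fold, arises only if unadjusted counts over 4 and 10 weeks are compared. All power figures rest on assumed AE rates and are illustrations.

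**What to change.** Restate the Appendix 9 sentence so that, at each review, the safety officer and the DSMB compare AEs per unit of participant-time between MC-CBT, S-CBT and ACC, separately for the treatment phase and for follow-up, overall and by site. Keep any change from baseline as supporting information only, expressed as a rate over a defined window. State when AE recording starts, and reconcile the visit marks in Appendix 7 with the recording rule in Appendix 5.

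The cost is the rewording of one paragraph, a clarification of the schedule, and a by-arm table in the DSMB reports that the data coordinating centre already prepares (Appendix 3).

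There are two downsides. By-arm summaries must be kept from site staff, including the study gastroenterologists, who rate outcome blind to allocation (Appendix 8). The S-CBT comparison must also be read with its greater contact in mind: ten sessions, against four sessions and two calls in both MC-CBT and ACC, give more opportunity to report events.
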